9.2 Tumor measurement

At baseline, the investigator will classify the lesions as measurable lesions (lesion with at least one precise longest diameter measurement ≥ 20 mm by CT or MRI or at least one precise longest diameter measurement ≥ 10 mm by spiral CT) and non-measurable lesion (solid lesion, bone lesion, meningeal lesion, pleural effusion and ascites, pericardial effusion lower than the aforementioned threshold for measurable lesions; abdominal masses and cystic lesions that cannot be confirmed and evaluated by routine radiologic techniques) based on RECIST 1.1 and irRECIST criteria.

The target lesions should involve affected organs. At most 5 target lesions should be recorded for every organ, and the total number of all target lesions should not exceed 10. Measurement and recording will be performed at baseline and all stipulated time points. Target lesions should be selected based on size (lesions with the largest diameter) and suitability for repeated accurate measurements (radiologic or clinical method). A primary lesion can only be classified as a target lesion if it can be accurately measured.

The longest diameter of every target lesion should be recorded. The longest diameters of all target lesions and their sum will be calculated and recorded. During treatment, the sum of the longest diameters at baseline will be used as a reference to determine the objective response of measurable tumors.

All non-measurable lesions and other measurable lesions that are not selected as target lesions should be identified as non-target lesions and recorded at baseline. The measurement data of these lesions are not required, but the presence and disappearance of these lesions during the entire study should be tracked.

The same technique and method should be used for pretreatment baseline measurement and efficacy assessment. CT, MRI, and other measurement methods with high repeatability and ease of data storage should be used.

During overall response evaluation, ultrasound should not be used to measure tumor lesions that are clinically difficult to measure (such as visceral lesions). Ultrasound evaluation can be considered an alternative for clinical evaluation of superficial palpable lymph nodes, subcutaneous nodules, and thyroid nodules. Ultrasound examinations also help confirm the complete disappearance of superficial lesions usually evaluated via clinical examination.

An increase in tumor markers does not constitute objective evidence of tumor exacerbation. However, a radiologic examination should be immediately repeated if there is an increase in these tumor markers to confirm whether an objective worsening has occurred.

9.3. Tumor response evaluation (measurable lesions)

- Target lesion:

Complete response (CR): Disappearance of all visible lesions after baseline evaluation, the absence of new lesions, tumor markers decrease to normal levels and maintained for 4 weeks;

Partial response (PR): The sum of maximum diameters of all target lesions decreased $\geq 30\%$ compared to baseline, the absence of new lesions maintained for 4 weeks;

Stable disease (SD): Changes in the sum of maximum diameters of all target lesions is between PR and PD;

Progressive disease (PD): The sum of maximum diameters of all target lesions increased $\geq 20\%$ compared with the sum in original target lesions (including baseline) or occurrence of a new lesion.

- Non-target lesion:

CR: Complete disappearance of non-target lesions after the baseline period and tumor markers decrease to normal levels;

Non-CR/non-PD: Presence of one or more non-target lesion; “stable or decreased”;

PD: Overall worsening of existing measurable lesions or confirmed progression or appearance of one or more new lesions.

When measurable tumors satisfy the response or stable (SD) criteria during the treatment period, cytological confirmation is mandatory for all cancer sources causing an occurrence or worsening of an effusion to distinguish between a response and SD or PD.

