4.1 Inclusion criteria

- (1) Women aged > 18 years;
- (2) Histologically confirmed endometrial cancer;
- (3) Recurrent or advanced endometrial cancer with at least one treatment with systemic platinum-based chemotherapy;
 - Low chance of a cure for recurrent endometrial cancer with surgery and/or radiotherapy and failure of at least one treatment with systemic platinum-based chemotherapy after recurrence.
 - Newly diagnosed advanced endometrial cancer persisting after standard treatment with surgery \pm radiochemotherapy and at least one treatment with systemic platinum-based chemotherapy.
- (4) Objectively measurable lesions based on RECIST 1.1 criteria and at least one target lesion;

- In principle, lesions in the field of previous radiotherapy are considered as non-target lesions unless there is radiological evidence of progression or a biopsy with progression within 90 days after radiotherapy.
- (5) Eastern Cooperative Oncology Group (ECOG) score of 0–2;
- (6) Expected survival >3 months;
- (7) Major organ function fulfills the following criteria (correction of the following parameters and supportive treatment are allowed 1 week before enrollment);
 - Absolute neutrophil count $\geq 1.5 \times 10^9/L$, platelet count $\geq 70 \times 10^9/L$, hemoglobin $\geq 80g/L$
 - Alanine transaminase (ALT) and aspartate transaminase (AST) $\leq 2.5 \times$ upper limit of normal (ULN) ($<5 \times$ for patients with liver metastases) and total bilirubin $\leq 1.5 \times$ ULN
 - Serum creatinine $\leq 1.5 \times$ ULN
 - International normalized ratio (INR) $<1.5 \times$ ULN
 - Proteinuria $\leq (+)$
 - Thyroid-stimulating hormone (TSH) $\leq 1 \times$ ULN (measure FT3 and FT4 if TSH abnormal; subjects with normal FT3 and FT4 can be enrolled)
- (8) Voluntarily signed informed consent form.

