9.1. Tumor imaging and disease evaluation principles

Tumor radiologic examinations usually include contrast-enhanced CT or MRI. The examination sites must include the chest, abdomen, and pelvic cavity. Cranial MRI scans must be performed at baseline for patients with suspected signs or symptoms of central nervous system metastases. Radiologic examinations received by a subject during the study period should be of the same type. Radiologic examinations will be performed on other suspected affected sites (such as the cranium) based on the subject's clinical signs and symptoms. Contrast-enhanced CT is the tumor evaluation method of choice. MRI will be used if contrast-enhanced CT is contraindicated. Slices of 10 mm or thinner are used for chest, abdominal, and pelvic CT and MRI scans, and 5 mm slices for continuous spiral CT scans. For clinically measurable superficial lesions (such as skin nodules, palpable lymph nodes), a color photograph containing a scale to show the lesion dimensions used to estimate lesion size is recommended.

During the screening, the study site investigator will confirm the presence of measurable lesions based on RECIST1.1 and irRECIST criteria to confirm the subject's eligibility. There should be a maximum of 5 target lesions in total and 2 target lesions per organ.

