9.5. Overall response determination

Overall evaluation of disease response involves all parameters listed in the following table. The best overall response refers to the best response recorded from the start of treatment to disease progression/recurrence (the lowest measurement recorded since the start of treatment is used as a reference for determining tumor worsening). The best response of the patient is determined by the measurement method and confirmation criteria.

Table 8. Timepoint efficacy determination based on irRECIST criteria.

Overall efficacy evaluation:

Target lesion	Non-target lesion	New lesion	Overall response
CR	CR	None	CR
CR	Non-CR/SD	None	PR
PR	PD absent	None	PR
SD	PD absent	None	SD
PD*	Any response	Present or absent	PD
Any response	PD	Present or absent	PD
Any response	Any response	Present	PD

*Reconfirmation according to irRECIST criteria is required

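### Section 9.3 defines target-lesion progression by a 20% rise with no minimum in millimetres, so in patients with small tumour sums measurement error alone can produce RECIST 1.1 progression.

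*Protocol*

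**What the plan says.** Four statements in the protocol act together.

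- Section 9.3 (target lesions): progression is a rise of at least 20% in the sum of maximum diameters "compared with the sum in original target lesions (including baseline) or occurrence of a new lesion". No figure in millimetres accompanies the percentage there or elsewhere in the text at hand.
- Section 9.2: a lesion is measurable with "at least one precise longest diameter measurement ≥ 10 mm by spiral CT".
- Section 4.1, criterion 4: entry needs "Objectively measurable lesions based on RECIST 1.1 criteria and at least one target lesion". The smallest possible baseline sum is therefore 10 mm.
- Section 9.5 (Overall response determination): "the lowest measurement recorded since the start of treatment is used as a reference for determining tumor worsening".

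Section 2.2 assesses PFS, DoR and DCR by both irRECIST and RECIST 1.1. The definition of DCR in section 9.4 names RECIST 1.1 only. Section 9.1 has the investigator record RECIST 1.1 alongside irRECIST but not use it to guide treatment. A footnote to Table 8 requires reconfirmation of target-lesion progression under irRECIST, and section 9.1 places the confirmatory scan 4-6 weeks later. No corresponding step is stated for RECIST 1.1.

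**The concern.** A purely relative threshold shrinks with the tumour. At the smallest sums the protocol admits, the change that counts as progression is one or two millimetres, which ordinary reading variation can produce. Taking the lowest earlier reading as the reference makes this worse, because a chance low reading becomes the standard for every later scan.

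Progression is an event for PFS and DoR, and progression at the first scan is a DCR failure. False calls would shorten RECIST 1.1 PFS and DoR, and would do so selectively in patients with low tumour burden. The wording of the reference adds to the problem. Section 9.3 points to the original sum including baseline, section 9.5 points to the lowest value, and the two give very different false-progression rates.

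**Working it through.** The protocol gives no error rate for its progression rule, so there is no stated figure to reproduce. The sample size of 23 does not depend on this point.

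**Step 1: trigger in millimetres.** Trigger = 0.20 × reference sum.

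- 10 mm: 0.20 × 10 = 2.0 mm
- 15 mm: 3.0 mm
- 20 mm: 4.0 mm
- 25 mm: 5.0 mm
- A 10 mm lesion after a 30% response: nadir 10 × 0.70 = 7 mm, trigger 0.20 × 7 = 1.4 mm

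**Step 2: model for a truly stable lesion.** One target lesion of true size T. Baseline reading B = T + error, and four follow-up readings X1 to X4 = T + error. Errors are independent and normal with SD σ. The protocol gives no reading error, so σ = 1 mm is an assumption, with 0.5 to 1.5 mm as the range. A patient is kept only if B ≥ 10 mm, because a smaller reading is not measurable under section 9.2. False progression is Xj ≥ 1.2 × R at any scan, where R is either B or the lowest earlier reading. I used 400,000 simulated patients per cell before applying the entry rule.

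**Step 3: chance of at least one false progression in four scans, σ = 1 mm.**

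| True size | Reference = baseline | Reference = nadir |
|---|---|---|
| 10 mm | 2% | 38% |
| 12 mm | 14% | 34% |
| 15 mm | 8% | 18-19% |
| 20 mm | 2% | 4% |

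For 10 mm against the nadir, the range is 3% at σ = 0.5 mm to 63% at σ = 1.5 mm. The baseline column is low at 10 mm because only lesions that happened to read high enter, so later readings tend to fall. Those lower readings then become the nadir, which is why the nadir column is high.

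**Step 4: after a response.** Take a 7 mm nadir and a fixed 1.4 mm trigger. The chance that one later reading exceeds the nadir reading by the trigger, with no true change, is P(difference ≥ 1.4), where the difference has SD √2 × σ. At σ = 1 mm this is P(Z ≥ 1.4/1.414) = 16.1%. It is 2.4% at σ = 0.5 mm and 25.5% at 1.5 mm. This bears on DoR.

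**Step 5: first scan only.** Here the nadir is the baseline. At σ = 1 mm, false progression among eligible readings is about 0.5% at 10 mm, 5% at 12 mm and 3% at 15 mm. This is the part that can turn stable disease into a DCR failure.

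**Step 6: with a minimum added.** Require also that Xj − nadir ≥ 5 mm. The minimum binds whenever the reference is below 25 mm (0.20 × 25 = 5). The four-scan rate falls to about 0.1-0.2% at σ = 1 mm and 5-7% at σ = 1.5 mm for lesions of 10 to 20 mm.

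**The case against.** The strongest reply is that the endpoints are assessed by RECIST 1.1 and irRECIST by name, and that the table of contents lists an Appendix 2 with RECIST 1.1 excerpts. Its text was not in the material reviewed. If it contains an absolute minimum, section 9.3 is an incomplete summary that conflicts with the appendix, and trial staff may never have applied the bare 20% rule. That stands as a limit on the finding. It does not remove it, because the two texts would still have to be reconciled.

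Confirmation also helps. For irRECIST it is required, so a 2 mm change counts there only if it is seen again. For RECIST 1.1, section 9.1 lets an investigator who is unsure of progression wait for a later scan, but that is discretionary. The protocol does not say that the first RECIST 1.1 reading is final. It simply states no reconfirmation.

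The effect is confined to small sums. Section 9.2 prefers the largest lesions as targets, and at 20 mm with σ = 1 mm the rate is 2-4%.

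A reader might infer more than the documents support:

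- **A rate of 24-50% for a 10 mm lesion.** That results from ignoring the entry rule. Half of the simulated patients would then have baseline readings below 10 mm and would not qualify.
- **Lost responders in the primary ORR.** An early false progression does close the best-response window, but the model describes stable lesions, which are non-responders either way. The loss in responders is not quantified, and the first-scan rates in step 5 suggest that it is small.
- **A change smaller than the slice is noise.** Section 9.1 specifies slices ("and 5 mm slices for continuous spiral CT scans"), but slice thickness is not the error of an in-plane diameter.
- **A defect in nodal response.** Section 9.2 says "The longest diameter of every target lesion should be recorded", and complete response in section 9.3 needs "Disappearance of all visible lesions after baseline evaluation". A node that shrinks by 30% or more but stays visible is still a partial response, so ORR and the other listed endpoints do not change. Nothing in the documents supplies a nodal rule to put in its place.

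**Conclusion.** The point holds for the rule as printed. A 2 mm rise from a 10 mm sum, or 1.4 mm from a 7 mm nadir, meets target-lesion progression in section 9.3. The exposure lies in the RECIST 1.1 versions of PFS and DoR and, through the first scan only, DCR. At an assumed reading SD of 1 mm, the four-scan false-progression rate against the nadir runs from about 38% at 10 mm to about 4% at 20 mm. The result is sensitive to the SD: 3% to 63% at 10 mm across 0.5 to 1.5 mm.

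These figures assume a single stable lesion, independent normal errors and an eligible baseline reading. The share of patients with such small sums cannot be derived from the protocol, so no overall bias in median PFS or DoR can be stated. The sample size is unaffected, and no material effect on the primary ORR has been shown. This is worth correcting because the correction is cheap, but it does not undermine the design.

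**What to change.** In section 9.3, add a second condition to target-lesion progression for the endpoint derivation: an absolute increase in the sum over the lowest on-treatment value, for example at least 5 mm, together with the 20% rise. The 5 mm is illustrative, since the text at hand gives no figure. In the same sentence, name the nadir (the lowest sum, baseline included) as the reference, so that section 9.3 agrees with section 9.5 (Overall response determination). Then check section 9.3 against the RECIST 1.1 criteria it relies on and against Appendix 2, and resolve any difference. State whether RECIST 1.1 progression needs confirmation for PFS, DoR and DCR. Decisions to stop treatment are a separate clinical matter and are not addressed here.

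The cost is one or two sentences and a change to the case report form derivation. The downside is that a small true progression may be dated one scan later.

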9.5. Overall response determination

Overall evaluation of disease response involves all parameters listed in the following table. The best overall response refers to the best response recorded from the start of treatment to disease progression/recurrence (the lowest measurement recorded since the start of treatment is used as a reference for determining tumor worsening). The best response of the patient is determined by the measurement method and confirmation criteria.

Table 8. Timepoint efficacy determination based on irRECIST criteria.

Overall efficacy evaluation:

Target lesion	Non-target lesion	New lesion	Overall response
CR	CR	None	CR
CR	Non-CR/SD	None	PR
PR	PD absent	None	PR
SD	PD absent	None	SD
PD*	Any response	Present or absent	PD
Any response	PD	Present or absent	PD
Any response	Any response	Present	PD

*Reconfirmation according to irRECIST criteria is required

9.4 Endpoint criteria

Primary endpoint:

Objective response rate (ORR): Defined as the proportion of patients whose tumor volume shrunk to the pre-stipulated value and maintained for more than 4 weeks; i.e., ORR = CR +

PR. The internationally accepted RECIST 1.1 and irRECIST criteria are used for solid tumor evaluation. ORR is used as the primary endpoint for the clinical trial.

Secondary endpoints:

Duration of response (DoR): Time from first evaluation of CR or PR until evaluation of PD or death from any cause. For patients who did not experience PD or death, the last radiologic tumor evaluation date will be the censor date.

Disease control rate (DCR): The proportion of subjects with CR, PR, or SD based on RECIST 1.1 criteria in the analysis set.

Time to response (TTR): Time from start of treatment to first objective response (CR or PR). For patients that did not experience CR or PR, the last radiologic tumor evaluation date will be the censor date.

Progression-free survival (PFS): Defined as time from subject enrollment to tumor progression or death.

Overall survival (OS): Time from start of treatment to death. If the subject is still alive at the end of the study, the “last known date of subject survival” will be the censor date.

12-month OS rate: The proportion of patients that are alive at month 12 after starting treatment.

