7.2. Prohibited concomitant therapies

The following treatments are prohibited during the study treatment period, and the subject must be asked whether he/she has received any new drug at each visit.

- Systemic chemotherapy or biologic therapy other than the study drug that has antineoplastic effects (except for cytokines used to treat adverse events caused by chemotherapy) and Chinese patent medicine with antineoplastic effects.
- Drugs with immunoregulatory effects, including but not limited to non-specific immunoregulators (e.g., thymosin, interferon, interleukin, immunoglobulin, gamma globulin), and Chinese patent medicines with immunoregulatory effects.
- Chemotherapeutic agents that are not stipulated in this protocol.
- Investigational drugs other than sintilimab.
- Radiotherapy used to control tumors (palliative radiotherapy is permitted as long as it is not used for the target lesion, such as radiotherapy for alleviating pain from bone metastases and symptoms of brain metastases).
- Live vaccines during the study. Injections of inactivated influenza vaccine for seasonal influenza are permitted, but live attenuated influenza vaccines for intranasal use are prohibited.
- Corticosteroids. Inhalational steroids are permitted for patients with asthma or chronic obstructive pulmonary disease. Corticosteroids are permitted for temporary use to alleviate dyspnea. Corticosteroids are permitted for the treatment of immune-related AEs. Note: Prophylactic use of corticosteroids to prevent anaphylaxis (e.g., pretreatment before intravenous administration of contrast agent or chemotherapy drug) is permitted.
- Prohibited drugs mentioned in the exclusion criteria.

8. Schedule of Events

This trial comprises three stages (screening period, treatment period, and end of treatment) after each patient signs the informed consent form.

8.1. In the screening period (Day-28 to Day-1), the following study procedures must be completed to ensure that the subject is eligible for this study:

- The informed consent form has been signed;

- Review of inclusion and exclusion criteria;
- Medical history including but not limited to demographic data, past medical history, past treatment history for endometrial cancer, and past and concomitant medications.
- Physical examination: height, weight, body surface area, vital signs (heart rate, blood pressure), comorbidities, and other discomforts;
- ECOG scoring;
- Electrocardiography (within 3 days before the 1st dose)

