11.1 Definition of statistical analysis sets

Full analysis set (FAS): Analysis of all enrolled patients who took at least one dose of the drug will be performed according to the intent-to-treat principle. The last observation carried forward is used for patients whose data were not captured for the entire duration of the study.

Per-protocol set (PPS): All patients who completed 2 cycles or more of treatment, conformed to the study protocol, had good compliance, did not use prohibited drugs during the study, and whose case report forms are completed as required. No imputation will be performed for missing data. Statistical analysis of FAS and PPS are simultaneously performed for drug efficacy analysis.

Safety analysis set (SAS): All enrolled patients who had at least taken one dose of the study drug and whose safety after drug administration had been recorded. This dataset will be used for safety analysis.

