11.2. Statistical analysis plan

Baseline data will be analyzed based on the FAS. Full analysis set (defined as all included patients) and safety analysis set (defined as patients had at least one cycle of treatment) were used for efficacy analysis and safety analysis, respectively. In general, categorical data will be summarized using number of patients (n), frequency and percentages. Two-sided exact 95% confidence intervals (CIs) based on the Clopper-Pearson method will be provided to summarize the binomial proportion of the ORR and DCR for both RECISTv1.1 and irRECIST assessments where applicable. Continuous data will be summarized using the number of patients, mean, standard deviation, median, first and third quartiles (Q1, Q3), minimum, and maximum. Time-to-event analyses will be performed using Kaplan-Meier (KM) methods. Medians of PFS and DOR were analyzed using the Kaplan-Meier curve, and 95% CIs were calculated with a generalized Brookmeyer and Crowley method. We calculated the probabilities of patients achieving a PFS > 6 months or > 12 months using the Kaplan-Meier product-limit method, and reverse Kaplan-Meier calculated the Greenwood Formula Follow-up time. Cox regression models were used to test the association between clinicopathologic and genetic characteristics and PFS, and a P-value < 0.05 was considered significant. For genomic analysis, P-value < 0.1 was considered statistically significant. All statistical analyses

about clinical listings will be performed using SAS v9.4 or higher. Gene analysis will be performed using R V4.1.0 or higher

12. Ethical Standards

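### PFS is timed from enrolment but OS and TTR from first dose, and TTR non-responders are censored even after confirmed progression or death

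*Protocol*

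**What the plan says.** **Time origins (Section 9.4).** PFS is "Defined as time from subject enrollment to tumor progression or death". OS is "Time from start of treatment to death". TTR and the 12-month OS rate also begin when treatment starts.

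**Enrolment and first dose as separate events.** Section 11.1 defines the full analysis set as "all enrolled patients who took at least one dose of the drug". The exclusion criteria in Section 4.2 count some windows back from enrolment (thrombosis, gut perforation) and others from the first dose (antineoplastic drugs, live vaccine). No section defines the enrolment date or says that it is the dosing date.

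**Analysis set.** Section 11.1 requires a dose. Section 3.1 puts every enrolled subject into the efficacy analysis, and Section 11.2 describes the full analysis set as all included patients.

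**TTR censoring (Section 9.4).** "For patients that did not experience CR or PR, the last radiologic tumor evaluation date will be the censor date". No exception is made for progression or death.

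**Method (Section 11.2).** "Time-to-event analyses will be performed using Kaplan-Meier (KM) methods". No competing-risk method is named. Medians are specified for PFS and DOR, not for TTR.

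**When response can be credited.** The section on overall response determination counts best response only up to progression. Section 9.1 allows treatment to continue after a first progression under irRECIST, with a confirmatory scan 4 to 6 weeks later.

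**The concern.** Death is an event for both PFS and OS, so on one clock PFS can never exceed OS. With PFS started earlier than OS, it can, and the listing for such a patient would be internally impossible. Under the Section 11.1 set, a patient must survive to her first dose in order to be counted. The interval from enrolment to dose is then event-free by construction and is added to PFS. PFS and its 6- and 12-month probabilities are named secondary results in the synopsis.

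The TTR rule is a separate problem. Kaplan-Meier assumes that a censored patient would go on to respond at the rate of those still under observation. That cannot be true of a patient with confirmed progression or of one who has died. A TTR curve built on this rule describes a setting in which nobody leaves through progression or death, and it can sit above the response proportion that the trial reports as its primary result.

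**Working it through.** **Design figure, for reference.** The stated two-stage rule (7 then 16 patients; stop at 1 or fewer responses; reject at 5 or fewer of 23) has

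P(pass) = sum over x = 2 to 7 of b(7, x, p) × P(Bin(16, p) ≥ 6 − x).

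This gives 0.0456 at p = 13% and 0.8003 at p = 39%, matching the stated alpha of 0.05 and power of 0.80. It uses only response counts, so neither issue below touches it.

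**Part 1: PFS against OS.** Let g be the days from enrolment to first dose.

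- Measured from first dose, a patient progresses (or dies without progression) at time t and dies at time d.
- As written, PFS = t + g and OS = d, so PFS exceeds OS whenever d − t < g. For death without progression, t = d, and any g > 0 is enough.
- Example, death on day 150 without progression: OS = 150 days. PFS = 151, 153 or 157 days for g = 1, 3 or 7.

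The size of g is an assumption, bounded by the text:

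- Section 12.1 places consent before enrolment, so enrolment is not consent.
- Section 8.1 has the blood, urine and coagulation tests that feed the organ-function criteria done within 3 days before the first dose. Footnote 11 to Table 1 does the same for the pregnancy test.
- If enrolment follows completed eligibility, g is therefore about 0 to 3 days.

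To size the shift, take the 5.4-month median PFS that Section 1.4 cites for sunitinib, with 30.4 days per month: 5.4 × 30.4 = 164 days.

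- Shift at g = 3: 3/164 = 1.8%. At g = 7: 7/164 = 4.3%.
- Exponential model from first dose, no events in the gap, S(m) = 2^(−m/5.4), with m reduced by g/30.4:

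| Landmark | g = 0 | g = 3 | g = 7 |
|---|---|---|---|
| 6-month PFS | 2^(−6/5.4) = 46.3% | 2^(−5.901/5.4) = 46.9% | 2^(−5.770/5.4) = 47.7% |
| 12-month PFS | 2^(−12/5.4) = 21.4% | 2^(−11.901/5.4) = 21.7% | not shown |

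**Part 2: TTR.** Scans after cycles 2, 4 and 7 (Section 9.1) fall at weeks 6, 12 and 21. The following counts are an assumed illustration for 23 patients, with every progression taken as confirmed:

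| Week | At risk | Responses | Progressions |
|---|---|---|---|
| 6 | 23 | 5 | 5 |
| 12 | 13 | 3 | 4 |
| 21 | 6 | 1 | 3 |

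- Observed response proportion: (5 + 3 + 1)/23 = 9/23 = 39.1%.
- Rule as written, 1 − KM: 1 − (18/23)(10/13)(5/6) = 1 − 900/1794 = 49.8%.
- Progression as a competing event: 5/23 + (13/23)(3/13) + (6/23)(1/6) = 9/23 = 39.1%.

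The last scan may instead be the confirmatory one. At 4 weeks after first progression, the patients progressing at weeks 6 and 12 are censored at weeks 10 and 16, the risk sets do not change, and the result is again 49.8%. At 6 weeks, those progressing at week 6 are still at risk at week 12, and the risk sets become 23, 18 and 6: 1 − (18/23)(15/18)(5/6) = 1 − 75/138 = 45.7%.

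Other assumed patterns with 9 responders among 23, with progressions at weeks 6/12/21:

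| Responses | Progressions | 1 − KM |
|---|---|---|
| 4/3/2 | none censored before week 21 | 39.1% |
| 6/3/0 | 5/4/5 | 44.6% |
| 6/3/0 | 8/4/2 | 50.7% |
| 4/3/2 | 5/4/5 | 53.6% |
| 4/3/2 | 8/4/2 | 70.0% |

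**The case against.** On PFS, the opposing case is that the gap is a few days at most, that the inversion vanishes if enrolment and first dose coincide, and that enrolment is a proper intention-to-treat origin if every enrolled patient is analysed, as Sections 3.1 and 11.2 suggest. A first-dose origin would be undefined for a patient who is never dosed. Most of this stands. The shift is probably small, and the event-free interval follows only from the Section 11.1 set. What remains is that Section 9.4 uses two origins for endpoints that share an event, and nothing in the protocol reconciles them.

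A reader might infer a shift of up to 28 days, since screening in Section 8.1 runs from Day −28; that would be 28/164 = 17% of the 5.4-month median. The documents do not support this, because consent precedes enrolment and the eligibility tests fall within 3 days of dosing.

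On TTR, the opposing case is that no TTR median or curve is called for by name, that ORR is estimated separately with an exact interval, and that a patient at first progression may still respond under irRECIST. All three are correct. A reader might infer that a reported response rate is inflated, or that every progressing patient is wrongly censored. Neither follows. The problem concerns confirmed progression and death, and it arises only if TTR is analysed by Kaplan-Meier. The general sentence in Section 11.2 leads there, however, and a censor date for non-responders has no purpose in a responders-only summary. The censoring sentence also does not separate patients who may still respond from those who cannot.

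**Conclusion.** Wrong as written, for secondary endpoints only.

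- **PFS.** The mixed origin is certain on the text. Its numerical effect rests on the undefined gap: about 0 to 3 days if enrolment follows the eligibility tests, which is up to about 2% of a 5.4-month median and about half a percentage point on 6-month PFS under an exponential curve. The logical fault, PFS longer than OS in the same patient, needs only a gap of one day.
- **TTR.** The size depends on when progressions and responses occur. The excess is zero if no non-responder is censored before the last response. The assumed patterns in which some non-responders left earlier gave 44.6% to 70.0% against 39.1%. It would be wrong to say that the curve always overstates response; it does so whenever patients with confirmed progression or death are censored before later responses.

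ORR, its Clopper-Pearson interval and the two-stage decision rule are unaffected.

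**What to change.** Two changes in Section 9.4:

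1. Define PFS from the start of treatment, the origin already used for OS, 12-month OS and TTR. This fits the dosed set in Section 11.1. The descriptions of the set in Sections 3.1 and 11.2 should be brought into line, because a first-dose origin has no meaning for an undosed patient.
2. Delete the TTR censoring sentence. Either summarise TTR in responders only (median and range), or show the cumulative incidence of response with confirmed progression or death before response as competing events.

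No new data or visits are needed. The one downside is that reported PFS becomes shorter by the enrolment-to-dose gap, probably a few days at most.
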